12 OCT2020

## 17.4 Protocol Amendments

### Version 2.1 dated 12 OCT 2020

Date	Section	Change from	Change to	Justification
12OCT2020	Synopsis, Sections 1..2.4, 4.1, 8.2	Previous verbiage	Various revisions and additions of verbiage to document the DSMB change in dose for 50 mg daily dose during Part B of the study	DSMB meeting on 12 OCT 2020 advised for all patients in Part B to receive the 100 mg twice daily dose
12OCT2020	Synopsis	Unscheduled treatment visit	Monitoring safety visit	Clarification of visit name

Sponsor: Avalyn Pharma, Inc.; Protocol No.: AP01-002

1. Glossary of Abbreviations

Abbreviation	Description
ADR	Adverse Drug Reaction
AE	Adverse Event
ALT	Alanine Aminotransferase
AP01	Pirfenidone Solution for Inhalation
AST	Aspartate Aminotransferase
ATC	Anatomical Therapeutic Chemical
BAL	Bronchoalveolar Lavage
BMI	Body Mass index
CI	Confidence Interval
CRF	Case Report Form
CSR	Clinical Study Report
CTCAE	Common Terminology Criteria for Adverse Events
CV	Cardiovascular
DSMB	Data and Safety Monitoring Board
D _{LCO}	Diffusion Capacity for Carbon Monoxide
ECG	Electrocardiogram
eCRF	Electronic Case Report Form
ELF	Epithelial Lining Fluid
FAS	Full Analysis Set
FEV ₁	Forced Expiratory Volume in One Second
FOCBP	Female of Child-Bearing Potential
FVC	Forced Vital Capacity
GCP	Good Clinical Practice
GLM	General Linear Model
HRCT	High-Resolution Computed Tomography
ICH	International Conference on Harmonization

This document is confidential.

SAP Version: 3.0 (15JUL2021)
 Controlled Document ID: **3903A.01**, Effective Date 29-Oct-2018
 Filing requirements: TMF

Page 8 of 52

Statistical Analysis Plan

Sponsor: Avalyn Pharma, Inc.; Protocol No.: AP01-002

Abbreviation	Description
IP	Investigational Product
IPF	Idiopathic Pulmonary Fibrosis
KBILD	The King's Brief Interstitial Lung Disease
LCM	Leicester Cough Monitor
LCQ	Leicester Cough Questionnaire
Max	Maximum
MedDRA	Medical Dictionary for Regulatory Activities
Min	Minimum
MMRM	Mixed Model Repeated Measures
N/A or NA	Not Applicable
NCI	National Cancer Institute
PE	Physical Exam
PFT	Pulmonary Function Tests
PP	Per-Protocol/Per-Protocol Set
PRO	Patient Reported Outcomes
PT	Preferred Term
QOL	Quality of Life
QTcB	Bazett-Corrected QT Interval
QTcF	Fredericia-Corrected QT Interval
RV	Residual Volume
SAE	Serious Adverse Event
SAF	Safety Set
SaO ₂	Saturated Oxygen
SAP	Statistical Analysis Plan
SD	Standard Deviation
SI	Standard International System of Units
SOC	System Organ Class

This document is confidential.

SAP Version: 3.0 (15JUL2021)
 Controlled Document ID: **3903A.01**, Effective Date 29-Oct-2018
 Filing requirements: TMF

Page 9 of 52

Statistical Analysis PlanSponsor: Avalyn Pharma, Inc.; Protocol No.: AP01-002

Abbreviation	Description
SOP	Standard Operating Procedure
TEAE	Treatment Emergent Adverse Event
TFL	Tables, Figures and Listings
TLC	Total Lung Capacity
UIP	Usual Interstitial Pneumonia
VAS	Visual Analogue Scale
VC	Vital Capacity
WHO	World Health Organization

This document is confidential.

SAP Version: 3.0 (15JUL2021)
Controlled Document ID: **3903A.01**, Effective Date 29-Oct-2018
Filing requirements: TMF

Page 10 of 52

Statistical Analysis PlanSponsor: Avalyn Pharma, Inc.; Protocol No.: AP01-002

2. Purpose

The purpose of this statistical analysis plan (SAP) is to ensure that the data listings, summary tables and figures which will be produced, and the statistical methodologies that will be used, are complete and appropriate to allow valid conclusions regarding the study objectives.

2.1. Responsibilities

Syneos Health will perform the statistical analyses and is responsible for the production and quality control of all tables, figures and listings.

2.2. Timings of Analyses

An independent Data and Safety Monitoring Board (DSMB) will perform a review of safety data from the first 20 patients after Week 4 to confirm the safety of multiple dose administration. A decision to stop, continue or modify the study will be made based on this review. Throughout the course of the study, all serious adverse events (SAEs) will be sent to the DSMB for review.

An interim analysis will be performed at the completion of Part A. All endpoints will be analyzed and a full set of tables, listings and figures will be generated.

The final analysis of all safety and efficacy endpoints over Part A and Part B is planned after all patients complete the final study visit in Part B or terminate early from the study.

This document is confidential.

SAP Version: 3.0 (15JUL2021)
Controlled Document ID: **3903A.01**, Effective Date 29-Oct-2018
Filing requirements: TMF

Page 11 of 52

Statistical Analysis PlanSponsor: Avalyn Pharma, Inc.; Protocol No.: AP01-002

3. Study Objectives

3.1. Primary Objective

The primary objective is to evaluate safety and tolerability of treatment with AP01 given once or twice daily to patients with idiopathic pulmonary fibrosis (IPF) by monitoring adverse events (AEs) and post-dose spirometry.

3.2. Secondary Objectives

The secondary objectives include:

- To estimate the treatment effect of AP01 given 50 mg once daily and 100 mg twice daily on absolute change in % predicted forced vital capacity (FVC) in patients with IPF
- To estimate the treatment effect of AP01 given 50 mg once daily and 100 mg twice daily on absolute change in % predicted Diffusion Capacity for Carbon Monoxide (D_{LCO}) in patients with IPF
- To compare the safety and efficacy of 50 mg once daily vs 100 mg twice daily dosing to provide guidance on dosing regimens for future studies
- To estimate the treatment effect of AP01 given 50 mg once daily and 100 mg twice daily on change in Patient Reported Outcomes (PROs) and cough in patients with IPF
- To estimate the treatment effect of AP01 given 50 mg once daily and 100 mg twice daily on change in the extent of fibrosis and lung volumes as measured by High Resolution Computed Tomography (HRCT) scans in patients with IPF
- To evaluate the following exploratory measurements:
 - Correlation between weekly home spirometry measurements and in-clinic spirometry values
 - Correlation of extent of fibrosis and lung volumes as measured by HRCT at Baseline and Week 24 to other measures of clinical status, e.g. spirometry
 - Change from baseline in serum biomarkers of alveolar epithelial injury (CA19-9 and CA-125).

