### **10.1.4 Collecting and Recording AEs**

#### **10.1.4.1 Period of Collection**

All AEs will be collected from the time of informed consent through the final study visit. All AEs and SAEs should be treated as medically appropriate and followed until event resolution.

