5.4. Protocol Deviations

Protocol deviations will be collected and will be categorized as:

- Informed Consent
- Enrollment Criteria
- Dosing
- Concomitant Medications
- Visits/Procedures Required
- Visit Schedule
- Non-compliance
- Regulatory
- Laboratory
- Other

They will also be graded as Major or Minor.

This document is confidential.

SAP Version: 3.0 (15JUL2021)
Controlled Document ID: **3903A.01**, Effective Date 29-Oct-2018
Filing requirements: TMF

Page 20 of 52

Statistical Analysis PlanSponsor: Avalyn Pharma, Inc.; Protocol No.: AP01-002

Major protocol deviations are defined as a subset of protocol deviations that may significantly impact the completeness, accuracy, and/or reliability of the study data or that may significantly affect the subject's rights, safety or well-being. Major protocol deviations will be included in the Clinical Study Report (CSR). These include: Enrollment Criteria (violation of inclusion/exclusion criteria, Informed Consent (informed consent not provided), Dosing (study drug deviation), Non-compliance, Concomitant Medications (administration of prohibit medication) and Other Good Clinical Practice (GCP) deviations. All protocol deviations will be tracked and corrective live actions implemented.

Protocol deviations will be summarized by grade and category for each treatment group and overall in the following ways:

- Patients with Any Protocol Deviations (Major or Minor)
- Patients with Major Deviations Only
- Patients with Minor Deviations Only (i.e. excluding those patients with Major deviations).
- Protocol Deviations Attributable to COVID-19

All protocol deviations will be listed.

This document is confidential.

SAP Version: 3.0 (15JUL2021)
Controlled Document ID: **3903A.01**, Effective Date 29-Oct-2018
Filing requirements: TMF

Page 21 of 52

Statistical Analysis PlanSponsor: Avalyn Pharma, Inc.; Protocol No.: AP01-002

6. General Aspects for Statistical Analysis**6.1. General Methods**

Unless otherwise specified, all data will be summarized by treatment group and overall. A separate summary of data from Part A of will be provided in addition to a full study summary including both Part A and Part B data. Categorical data will be summarized as number and percent of total. Continuous data will be summarized using mean, median, SD and range. Dose response will be evaluated by comparing safety and changes in efficacy variables across the dose regimens.

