then subtracted from the time of nebulization. Time of nebulization will then be summarized for each dose by treatment group with descriptive statistics. In addition, the Time of nebulation will be summarized for just those patients who took the full dose with no interruptions for each dose by treatment group with descriptive statistics.

- To assess tolerance, the number of patients with a $\geq 15\%$ drop from pre-dose FEV₁ % predicted to post-dose FEV₁ % predicted will be summarized for each dose (first dose only if only 1 dose was received or for each dose if 2 doses are received) by treatment group with frequency counts and percentages (see more details in Section 10.6).

Post-Baseline: At Home

- For each patient, the treatment days will be derived cumulatively across all visits as the last dose date minus the first dose date + 1 and will be summarized by treatment group with descriptive statistics.
- For each patient, the actual total dosage (mg) of AP01 will be derived cumulatively across all visits across all patient doses as 50 times the total number of used ampoules returned, and will be summarized by treatment group with descriptive statistics.
- For each patient, the percent compliance will be derived cumulatively across all visits across all patient doses as 100 times (the total number of used ampoules returned divided by the total number of ampoules that would be used if they were fully dosing for the number of days between visits {slightly different from the number of ampoules dispensed}). If a subject discontinues early, the denominator will be the total number of ampoules, which would be used up to, and including the date of discontinuation. Percent compliance will be summarized by treatment group with descriptive statistics. The percent compliance will be categorized ($\geq 80\%$, 60- $<80\%$, 40- $<60\%$, 20- $<40\%$ and $<20\%$) and summarized by treatment group with frequency counts and percentages. The percent compliance will be calculated overall and separately for each dosing regimen for those patients who switch over from 50 mg once daily to 100 mg twice daily in Part B.

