10.1. Adverse Events / Adverse Drug Reactions

An adverse event (AE) is any untoward medical condition that occurs in a patient while participating in this clinical study. Adverse events will be coded according to the Medical Dictionary for Regulatory Activities (MedDRA 21.1 or higher) terminology and the severity of the toxicities will be graded according to the National Cancer Institute (NCI) Common Terminology Criteria for Adverse Events (CTCAE), v5.0, where applicable. An adverse drug reaction (ADR) means any AE caused by a drug or biologic.

Treatment-Emergent Adverse Events (TEAEs) are those adverse events/adverse drug reactions that are recorded during or following the initiation of AP01 medication administration, and do not necessarily have a causal relationship to the use of the study medication. Treatment-Emergent Adverse Events (simply referred to as adverse events in summary tables) will be summarized.

The following adverse event summary tables will be summarized by treatment group and combined over both treatment groups:

- 1) An overall summary with the number and percentage of patients reporting AEs, serious AEs, grade 3 or higher AEs, treatment-related AEs, AEs leading to study treatment (AP01) discontinuation and AEs with outcome of deaths. In addition, this overall summary will be performed for each subgroup listed in Section 6.6.
- 2) AEs overall and by system organ class and preferred term. In this summary, a patient is counted once at the system organ class and once at each preferred term within the system organ class. In addition, this summary will be performed for each subgroup listed in Section 6.6.
- 3) A separate summary of respiratory [SOC respiratory, thoracic and mediastinal disorders] TEAEs by Preferred Term and summary of tolerability including cough due to drug administration and bronchospasm after in-clinic drug administration) will be performed by each subgroup listed in Section 6.6.

This document is confidential.

Statistical Analysis PlanSponsor: Avalyn Pharma, Inc.; Protocol No.: AP01-002

- 4) AEs overall and by system organ class, preferred term and highest CTCAE grade.

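### Comparing the safety of the two regimens is a stated objective, but the SAP plans no between-arm estimate or interval for adverse events

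*SAP*

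**What the plan says.** - **Objective.** SAP 3.2, matching Protocol section 2, includes "To compare the safety and efficacy of 50 mg once daily vs 100 mg twice daily dosing to provide guidance on dosing regimens", with later trials in mind. SAP 6.1 adds: "Dose response will be evaluated by comparing safety and changes in efficacy variables across the dose regimens".
- **AE tables.** SAP 6.1 sets the general rule: "Categorical data will be summarized as number and percent of total". SAP 10.1 follows it: "The following adverse event summary tables will be summarized by treatment group and combined over both treatment groups". The first table is "An overall summary with the number and percentage of patients reporting AEs", with further categories. In the table by system organ class and preferred term, "a patient is counted once at the system organ class and once at each preferred term within the system organ class". SAP section 10 contains no risk difference, ratio, confidence interval, exposure-adjusted rate or time-to-event method.
- **Follow-up time.** SAP 7.5 summarises exposure by arm: "the treatment days will be derived cumulatively across all visits as the last dose date minus the first dose date + 1". SAP 7.1 tabulates disposition and reasons for discontinuation. Neither is connected to the AE tables. Protocol 10.1.4.1 sets the AE observation period: "All AEs will be collected from the time of informed consent through the final study visit". For a patient who terminates early, that period is shorter.
- **Precision.** The only safety precision figures (SAP 3.5, Table 1; Protocol 11.1, Table 10) give the chance of seeing at least one event among 50 patients.
- **Efficacy.** FVC % predicted (SAP 8.1), cough frequency (8.2.1) and HRCT (8.2.5) do get modelled differences between arms.

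**The concern.** The plan promises a randomised comparison of safety but names no quantity that would express it. A reader of the report will see two percentages side by side. At 50 per arm, two similar percentages invite a conclusion of similar tolerability when a sizeable excess in either direction has not been excluded.

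There is also a question of follow-up. Each table counts a patient as ever or never having had the event, over all patients in the arm. Someone who leaves early stays in the denominator although later first events can no longer be seen. The protocol has several exit routes that could differ by regimen: lack of efficacy or need for oral antifibrotic treatment in Part A, non-compliance, and persistent symptoms. The first two need not follow an AE. Protocol 8.2 itself expects the shorter regimen to bring more compliance and perhaps fewer respiratory effects, so unequal follow-up is foreseeable, though not established.

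**Working it through.** **1. The plan's own figure.** The chance of at least one event is 1 - (1 - p)^50. For p = 1%, 5% and 10% this gives 0.395, 0.923 and 0.995, as stated. It concerns one arm and says nothing about a difference between arms.

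**2. Precision of a difference at 50 per arm.** The Newcombe interval combines the Wilson limits (l, u) of each arm: lower limit = d - sqrt[(p1 - l1)^2 + (u2 - p2)^2], upper limit = d + sqrt[(u1 - p1)^2 + (p2 - l2)^2]. For 10/50 the Wilson limits are 11.2% and 33.0%. With 10/50 in both arms the half-width is sqrt(0.088^2 + 0.130^2) = 0.157. The documents give no AE rates, so a range of assumed counts follows.

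| 100 mg vs 50 mg (of 50 each) | Difference, points | 95% CI |
|---|---|---|
| 5 vs 5 | 0 | -12.7 to 12.7 |
| 10 vs 10 | 0 | -15.7 to 15.7 |
| 15 vs 15 | 0 | -17.5 to 17.5 |
| 25 vs 25 | 0 | -18.9 to 18.9 |
| 10 vs 5 | 10 | -4.3 to 24.2 |
| 13 vs 5 | 16 | 0.8 to 30.7 |
| 20 vs 10 | 20 | 2.0 to 36.4 |

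**3. Unequal follow-up.** All dropout and event rates here are assumptions. Let R be the risk with full Part A follow-up and D the proportion lost. Assume a constant event hazard and a constant loss hazard, with exit unrelated to the event. With l = -ln(1 - R) and m = -ln(1 - D), crude percentage = l/(l + m) x [1 - exp(-(l + m))].

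| R | D = 0 | D = 10% | D = 20% | D = 40% | D = 50% |
|---|---|---|---|---|---|
| 20% | 20.0 | 19.0 | 18.0 | 15.8 | 14.6 |
| 40% | 40.0 | 38.1 | 36.2 | 32.0 | 29.7 |
| 60% | 60.0 | 57.4 | 54.7 | 48.8 | 45.5 |

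At R = 40% in both arms, 10% loss in one and 40% in the other gives 38.1% against 32.0%, a false gap of about 6 points. A true hazard ratio of 1.25 in the arm losing 40% gives R = 1 - 0.6^1.25 = 47.2% and a crude 38.0%. Against 38.1% in the other arm, the excess disappears. With equal hazards and equal loss there is no gap.

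If instead 20% leave at Week 4, crude = 0.8R + 0.2[1 - exp(-4h)], where h = -ln(1 - R)/24. This gives 33.6% for R = 40% and 50.8% for R = 60%.

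**4. What step 3 does not cover.** In the Week 4 calculation at R = 40%, leavers have a prior event risk of 1 - exp(-4h) = 8.2%, so about 92% leave without the event. That is not dropout caused by the event. A patient who stops because of an AE has already been counted for it, and the crude percentage for that AE is not lowered. The loss is confined to other first events that would have come later, and to exits unrelated to the event.

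**The case against.** The case for leaving the plan alone has real substance.

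- **Purely descriptive safety tables are usual in Phase 1b, and SAP 6.1 plans no formal tests.** True, but an interval without a p-value is estimation, and this trial randomises and names the safety comparison as an objective.
- **Anyone can compute a risk difference from the tabulated counts.** This stands for the crude difference. It does not stand for cumulative incidence, which needs event and exit times, and it leaves the choice of categories to the reader.
- **Other comparative information exists.** Treatment days, compliance, discontinuation reasons and AEs leading to termination are tabulated by arm. Laboratory values, vital signs, oxygen saturation and FEV1 get descriptive statistics. Post-dose spirometry, taken within 10 minutes of the first dose, has no follow-up problem. This narrows the point to AEs.
- **Safety is not singled out.** KBILD, LCQ and cough VAS also get descriptive statistics only. That is correct, so the contrast with efficacy holds for FVC, cough frequency and HRCT, not across the board.

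A reader might go further and infer three things that the documents do not support. First, that the missing interval makes the comparison imprecise: the imprecision comes from 50 per arm, and an interval would only show it. Second, that intolerance itself pulls down the AE percentage of the less tolerated regimen: step 4 shows why it does not for the event that caused the exit. Third, that the regimen choice rested on these tables: the protocol synopsis and section 4.1 record the DSMB recommendation of 12 October 2020 as based on an FVC trend, and SAP version 3.0 is dated 15 July 2021.

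**Conclusion.** The concern holds in a limited form. A stated objective has no estimate attached to it for AEs, and the uncertainty of the comparison goes unreported. That uncertainty is roughly +/-13 points when both arms show 10%, +/-16 at 20% and +/-19 at 50%, assuming 50 evaluable patients per arm.

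The follow-up bias is conditional. Its direction is clear if follow-up differs between arms and exit is not itself the event counted: the arm followed for less time looks safer. Its size is unknown. The illustrative 6-point gap rests on assumed losses of 10% and 40%, constant hazards and exit unrelated to the event, and it is smaller than the +/-16-point sampling uncertainty at 20% in both arms.

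This is a cheap improvement worth making. It does not invalidate the planned tables.

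**What to change.** In SAP 10.1, add one table for Part A covering a fixed list: any treatment-emergent AE (TEAE), treatment-related TEAE, grade 3 or higher, SAE, TEAE leading to AP01 discontinuation, cough, and the respiratory system organ class.

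- Give the 100 mg minus 50 mg risk difference with a 95% Newcombe interval, labelled descriptive, with no p-value and no multiplicity adjustment.
- Beside it, not in its place, give the Week 24 cumulative incidence of first event by arm, with the difference and its 95% interval. Count events and time at risk over the same defined window, treat death as a competing event where relevant, and state that censoring is assumed non-informative. That assumption is doubtful when patients leave for intolerance, which is why the crude difference stays.
- Do not use events per patient-weeks on treatment unless the event window is matched to it. SAP 10.1 defines TEAEs with a start but no end, so numerator and denominator would not correspond. A rate also assumes a constant hazard, which early tolerability events would violate.
- State which arm grouping applies: SAP 5.1 groups the safety set by treatment received, while Protocol 11.2 analyses patients as randomised.
- Present the results as guidance for future studies, not as the basis of the October 2020 decision.

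The cost is a paragraph of SAP text and one table from data already collected. The drawback is a set of unadjusted intervals, which the descriptive label must make plain.

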3.3. Brief Description

This Phase 1b, 2-part, open-label study of AP01 will randomize approximately 100 patients with IPF. Patients will be randomized in a 1:1 ratio to one of two treatment groups: 50 mg once daily or 100 mg twice daily.

This document is confidential.

SAP Version: 3.0 (15JUL2021)
Controlled Document ID: **3903A.01**, Effective Date 29-Oct-2018
Filing requirements: TMF

[figure not shown]
Page 12 of 52

Statistical Analysis Plan

Sponsor: Avalyn Pharma, Inc.; Protocol No.: AP01-002

Figure 1: Part A Study Schema

PART A – Patients are randomized at Visit 2 to either 50 mg given once daily or 100 mg AP01 given twice daily

**Figure 2: Part B Study Schema**

PART B – Patients continue randomized treatment regimen of either 50 mg once daily or 100 mg AP01 twice daily

In Part A, eligible patients at least 40 years of age with a confident clinical and radiographic diagnosis of IPF according to pre-specified criteria, $40 \leq \%FVC \leq 90$, forced expiratory volume in 1 second (FEV_1)/FVC ratio $\geq 70\%$ and $30 \leq \%DL_{CO} \leq 90$ will be randomized with equal probability to receive AP01 50 mg once daily or 100 mg twice daily for 24 weeks. Other than brief periods of medically appropriate treatment for acute IPF exacerbation, patients will not receive any other therapy for the treatment of IPF during Part A. If in the opinion of the investigator, a patient is in need of treatment with oral pirfenidone or nintedanib during Part A, the patient should be discontinued from the study and return to the clinic for their Early Termination visit. Supplemental oxygen will be allowed during the entire study.

The initial dose of drug will be administered in the clinic to confirm airway tolerance. If based on the investigator's opinion, the patient had tolerability issues during the first dose administration, a second dose, at least 4 hours later, will also be observed. Patients who experience cough that limits their ability to complete dosing will be given 1 - 2 puffs (90 - 100 microgram (μg)) of salbutamol in order to complete the in-clinic dose. These patients, as well as patients with a history of asthma or smoking history of 20 pack years or greater, or patients that have a $\geq 15\%$ drop in FEV_1 % predicted in their pre-dose and post-dose readings will be required to use 1 - 2 puffs (90 - 100 μg) of salbutamol prior to

This document is confidential.

SAP Version: 3.0 (15JUL2021)
Controlled Document ID: **3903A.01**, Effective Date 29-Oct-2018
Filing requirements: TMF

Page 13 of 52

Statistical Analysis Plan

Sponsor: Avalyn Pharma, Inc.; Protocol No.: AP01-002

dosing throughout the study unless these patients are currently taking a long-acting beta-2-agonist therapy.

Patients will have a telephone assessment at Week 1 and in-clinic assessments at Weeks 4, 8, 12, 16, 20, and 24. The DSMB will perform a review of safety data from the first 20 patients after Week 4 to confirm the safety and airway tolerability of multiple dose administration. A decision to stop, continue or modify the study will be made based on this review.

Part B will collect long-term safety and efficacy data for an additional 48 weeks. Patients who complete Part A through Week 24 and, in the opinion of the investigator are compliant with treatment, may select to continue the treatment to which they were randomized. If one dosing regimen is determined to be superior either from an efficacy or safety standpoint, Part B may be converted to a single dose regimen and all patients who select to continue or start Part B at that point will be dosed with the selected regimen.

Study duration is up to 80 weeks for patients that complete both Part A and Part B of the study. If patients discontinue study treatment prior to Week 72 for any reason, they should return to the site for an Early Termination visit. All patients who complete the regular study visits through Week 72 in Part B will return for a Follow-up visit 28 days after their End of Study visit.

